10.2.2.2 Visit 2 (Day 15 ± 3 days)

1. Obtain information on any changes in medical health and/or the use of concomitant medications.
2. The unmasked site staff will perform drug accountability, record, and collect the kit(s) of masked study product.
3. Subjects should complete the following questionnaires:
 - [REDACTED]
 - Ocular Discomfort questionnaire
4. The following assessments must be completed in both eyes (OU) (see the MOP for details regarding each assessment and order of testing).
 - The BCVA must be measured using an ETDRS or Tumbling E chart at a distance of 3 or 4 meters using the letters read method. The test may be performed using the subject's historical correction. Visual acuity testing should precede any examination requiring diagnostic drops (eg. dilating drops) or contact with the eye.
 - Slit-lamp examination
5. The unmasked site staff will instill a single drop of the masked test/control product that was dispensed to the subject in each eye. Masked site personnel must not be present while the bottle of masked test/control product is removed from the kit and administered.
6. The following assessments must be completed in both eyes (OU) (see the MOP for details regarding each assessment and order of testing).
 - LLT assessment
 - TFBUT assessment
 - [REDACTED]
7. The unmasked site staff will dispense an additional masked study product kit.

8. Subjects will be instructed to continue to dose 1 drop of the test/control product in each eye QID. The last dose should be at bedtime (ie, no later than midnight).
9. Subjects will be instructed to retain and return all used and unused kits at their next visit.
10. Record any AEs that are observed or reported, including those associated with changes in concomitant medication dosing.
11. Schedule Visit 3 to take place 35 ± 3 days after Visit 1.
12. Provide subject with Treatment Phase Dosing Instructions card and provide Study Information card if original card is lost or unavailable.
13. Enter the subject information and visit data into the EDC system.

10.2.2.3 Visit 3/Final Visit (Day 35 ± 3 days)

1. Obtain information on any changes in medical health and/or the use of concomitant medications.
2. Conduct urine pregnancy test on women of childbearing potential.
3. Subjects should complete the following questionnaires:
 - 
 - Ocular Discomfort questionnaire
4. The following assessments must be completed in both eyes (OU) (see the MOP for details regarding each assessment and order of testing).
 - The BCVA must be measured using an ETDRS or Tumbling E chart at a distance of 3 or 4 meters using the letters read method. The test may be performed using the subject's historical correction. Visual acuity testing should precede any examination requiring diagnostic drops (eg. dilating drops) or contact with the eye.
 - Slit-lamp examination
5. The unmasked site staff will instill a single drop of the masked test/control product that was dispensed to the subject in each eye. Masked site personnel must not be present while the bottle of masked test/control product is removed from the kit and administered.
6. The following assessments must be completed OU (see the MOP for details regarding each assessment and order of testing).

- LLT assessments
 - TFBUT assessment
 - 
7. The unmasked site staff will perform drug accountability, record, and collect all kit(s) of study products.
 8. Record any AEs that are observed or reported, including those associated with changes in concomitant medication dosing.
 9. Exit the subject from the study.
 10. Enter the subject information and visit data into the EDC system.

10.3 Unscheduled Visits

Any visit that occurs between the regularly scheduled visits must be documented in the Unscheduled Visit pages of the case report form (CRF). During all unscheduled visits, the following procedures must be conducted:

1. Obtain information on any changes in medical health and/or the use of concomitant medications.
2. The following assessments must be completed OU (see the MOP for details regarding each assessment).
 - BCVA must be measured using an ETDRS or Tumbling E chart at a distance of 3 or 4 meters using the letters read method. The test may be performed using the subject's historical correction. Visual acuity testing should precede any examination requiring diagnostic drops (eg. dilating drops) or contact with the eye.
 - Slit-lamp examination.
3. Record any AEs that are observed or reported, including those associated with changes in concomitant medication dosing.
4. Unmasked site staff will collect and dispense masked study product kits as necessary.

Other assessments may be done at the discretion of the Investigator to appropriately treat the subject. If the subject is discontinuing at the unscheduled visit, the Early Exit CRFs should be completed rather than the CRFs for an Unscheduled Visit and the appropriate Exit procedure should be completed as described in the following sections.

10.4 Discontinued Subjects

Discontinued subjects are those who withdraw or are withdrawn from the study after the Screening Visit. Subjects may discontinue from the study at any time for any reason. Subjects may also be discontinued from the study at any time if, in the opinion of the Investigator, their continued participation poses a risk to their health. Discontinued subjects will not be replaced (ie, their subject numbers will not be re-assigned/re-used).

Should a subject exhibit any clinically relevant signs, symptoms, or other clinical observations that could be possibly associated with suspected sensitivity or intolerance to one of the study products, the Investigator must document those observations on an AE Form.

Any subject who exits early from the study (ie, prior to Day 35) must undergo all the procedures outlined at Early Exit in Section 0. Additionally, the Exit Form must be completed and one of the following reasons for discontinuation must be identified:

- Discontinued due to Screen Failure
- Discontinued due to AE
- Discontinued due to Death
- Discontinued due to Lost to Follow Up
- Discontinued due to Non-Compliance with Study Drug
- Discontinued due to Physician Decision
- Discontinued due to Pregnancy
- Discontinued due to Protocol Violation
- Discontinued due to Study Terminated by Sponsor
- Discontinued due to Technical Problems
- Discontinued study due to Withdrawal by Subject
- Discontinued due to Other Reason (specify)

Finally, to ensure the safety of all subjects who discontinue early, Investigators should assess each subject and, if necessary, advise them of any therapies and/or medical procedures that might be needed to maintain their health.

10.5 Clinical Study Termination

If the clinical study is prematurely terminated or suspended, the Sponsor will inform the Investigator and the regulatory authorities (if necessary) of the termination/ suspension and the reason(s) for the termination/suspension. The Investigator should promptly notify the IEC/IRB of the termination or suspension and of the reasons. The Sponsor reserves the right to close the study site or terminate the study in its entirety at any time, for reasonable cause. Reasons for the closure of a study site or termination of a study may include:

- Successful completion of the study
- The study's enrollment goals are met
- The Investigator fails to comply with the protocol or GCP guidelines
- Safety concerns
- Sufficient data suggesting lack of efficacy
- Inadequate recruitment of subjects by the Investigator

The Investigator may also terminate the study at his/her site for reasonable cause. If the Sponsor terminates the study for safety reasons, the Sponsor will immediately notify the Investigator(s) by telephone and will subsequently provide written confirmation of and instructions for study termination.

11 ANALYSIS PLAN

11.1 Subject Evaluability

All subjects who satisfy the inclusion and exclusion criteria, and who sign the informed consent form, will be considered evaluable.

The final subject evaluability will be determined prior to breaking the code for masked treatment assignment and locking the database.

11.2 Analysis Data Sets

Three analysis sets will be defined for this study: the Safety Analysis Set, Full Analysis Set (FAS) and Per Protocol Set (PPS).

The FAS will include all randomized subjects who have at least 1 post-baseline primary endpoint assessment.

The PPS will consist of FAS subjects who satisfy all inclusion/exclusion criteria and who have no major protocol deviations, which will be specified in the Deviations and Evaluability Plan (DEP).

The Safety Analysis Set will include all subjects exposed to post-randomization study product.

The primary and secondary efficacy analyses will be performed on both the FAS and PPS with the PPS providing the primary inference for the noninferiority hypothesis and the FAS providing the primary inference for the superiority hypotheses.

In the event of a randomization or dispensing error, subjects in the Safety Analysis Set will be analyzed according to the study product they received; however, subjects in the FAS will be analyzed as randomized (regardless of the study product they received).

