15. History of ocular or intraocular surgery, eyelid surgery, keratorefractive procedure, corneal transplant or serious ocular trauma, within 6 months prior to the Screening Visit
16. Initiation of any topical ocular (over-the-counter or prescribed) medication (with the exception of artificial tears/gels/lubricants) \leq 2 weeks prior to the Screening Visit

Assessments:

[figure not shown]
Screening:

The following assessments will be performed exclusively at the Screening Visit:

- Schirmer I test without anesthesia
- Intraocular pressure (IOP)
- Fundus examination (undilated)

Efficacy:

- Primary endpoint assessment: TFBUT
- Secondary endpoint assessments:
 - TFBUT
 - LLT (LLT AUC₁₂₀ at Day 35)
 - Global Ocular Discomfort questionnaire

Safety:

- Adverse events (AEs)
- BCVA
- Slit-lamp examination

Sponsor: Alcon Research, Ltd.
[name]
[name]

Protocol Number: EXB107-P001

Note: For eligible study subjects, all study assessments during each visit must be conducted at the same time of day within ± 1 hour of the start time of Visit 1 (Baseline).

[figure not shown]
Statistical Methods: Variables

Primary Endpoint

- Change from baseline in TFBUT at Day 35 (assessment for noninferiority)

Secondary Endpoints

- Change from baseline in TFBUT at Day 35 (assessment for superiority)
- LLT AUC₁₂₀ at Day 35
- Change from baseline in Global Ocular Discomfort VAS score at Day 35

Safety Variables

- AEs
- BCVA
- Slit-lamp examination

Planned Analyses

Three analysis sets will be defined for this study. The Full Analysis Set (FAS) will include all randomized subjects who have at least one post-baseline primary endpoint assessment. The Per Protocol Set (PPS) will consist of FAS subjects who have no major protocol deviations. The Safety Analysis Set will include all subjects exposed to post-randomization study product. In the event of a randomization or dispensing error, subjects in the Safety Analysis Set will be analyzed according to the study product they received; however, subjects in the FAS will be analyzed as randomized (regardless of the study product they received).

The primary and secondary efficacy analyses will be performed on both the FAS and PPS with the PPS providing primary inference for the noninferiority hypothesis and FAS providing primary inference for

Sponsor: Alcon Research, Ltd.
[name]
[name]

Protocol Number: EXB107-P001

the superiority hypotheses.

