2.4.2 Unscheduled visits

All data collected at unscheduled visits will be listed.

Adverse event (AE) and exposure to study treatment data collected at unscheduled visits will be used.

3 Analysis Sets

The **Screened Set (SCR)** will consist of all subjects who signed the informed consent form (ICF).

The **Randomized Set (RS)** will consist of all subjects who were randomized to one of the study treatment arms.

The **Full Analysis Set (FAS)** is used to describe the analysis set which is as complete as possible and as close as possible to the intent-to-treat (ITT) principle of including all randomized subjects. The FAS will include all randomized subjects who have at least 1 post-baseline primary endpoint (TFBUT) assessment.

The **Per Protocol Set (PPS)** will consist of FAS subjects who satisfy all inclusion/ exclusion criteria and who have no major PDs, which will be specified in the Deviations and Evaluability Plan (DEP).

The **Safety Analysis Set** will include all subjects exposed to post-randomization study product.

Evaluability for all subjects will be determined prior to breaking the code for masked study treatment assignment.

The primary and secondary efficacy analyses will be performed on both the FAS and PPS with the PPS providing the primary inference for the non-inferiority hypothesis and the FAS providing the primary inference for the superiority hypotheses.

Supportive analyses of the primary hypothesis will be conducted using the FAS. Similarly, supportive analyses of the secondary hypotheses will be conducted using the PPS.

The number of subjects excluded from the FAS and PPS and a listing of excluded subjects with reason for exclusion will be presented. Any inconsistencies in key study results between the FAS and PPS will be examined and discussed in the CSR.

All efficacy analyses will be according to randomized assignment (regardless of the study treatment they received).

Safety analyses will be conducted using the Safety Analysis Set on a treatment-emergent basis. The main safety analyses will focus on the investigational products (SYSTANE BALANCE, REFRESH OPTIVE Advanced/ OPTIVE PLUS [UK]). For treatment-emergent safety analyses, subjects will be categorized under the actual study treatment received.

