Evidence of efficacy (non-inferiority) will be deemed established if the lower limit of the 95% CI (equivalent to the 1-sided 97.5% CI) for the adjusted estimate of the difference (SYSTANE BALANCE - REFRESH OPTIVE Advanced/ OPTIVE PLUS [UK]) is above - 1.0 second (non-inferiority margin). The non-inferiority margin was chosen as 1.0 second on the basis that an increase of at least 25% in the baseline TFBUT of a subject with lipid-deficient dry eye would be considered clinically meaningful since the subject would blink less often.

The analysis set for the primary efficacy assessment will be the PPS. As a sensitivity analysis, the analysis will be repeated for the FAS using the same model.

Observed values and change from baseline values for the analysis eye for the PPS and FAS will also be presented descriptively (N, mean, median, SD, standard error [SE], minimum, and maximum) at each study visit for each study treatment. A plot of mean change in TFBUT by study visit and study treatment with error bars representing +/- 1 SE will be presented using the analysis eye. The x-axis will be study visit and the y-axis will be the change in TFBUT from baseline.

Observed values from all visits for the RS will also be listed along with the following variables: treatment, investigator, subject, age, sex, race, ethnicity, visit, eye, baseline value, and value at the visit.

The analysis of the secondary efficacy parameters will also be based on a MMRM model. The mixed model will include terms for the respective baseline parameter value (continuous), study treatment (SYSTANE BALANCE, REFRESH OPTIVE Advanced/ OPTIVE PLUS [UK]), visit (Day 15 [Visit 2], Day 35 [Visit 3]), and study treatment-by-visit interaction. The same procedure as outlined for the primary efficacy analysis in selecting the best fitting covariance structure will be applied. Estimates of the difference in mean change from baseline between SYSTANE BALANCE and REFRESH OPTIVE Advanced/ OPTIVE PLUS (UK) and the associated 95% CIs in the analysis eye will be presented.

Each secondary endpoint will be evaluated for superiority of SYSTANE BALANCE over REFRESH OPTIVE Advanced/ OPTIVE PLUS (UK).

The analysis set for the secondary efficacy assessments will be the FAS. As a sensitivity analysis, the analysis will be repeated for the PPS using the same model.

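### Entry to the FAS depends on TFBUT alone, so a randomised subject with a post-baseline discomfort VAS but no post-baseline TFBUT is left out of every VAS comparison

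*Protocol*

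**What the plan says.** **Entry to the FAS.** Protocol section 11.2: "The FAS will include all randomized subjects who have at least 1 post-baseline primary endpoint assessment". The protocol synopsis identifies the measurement: "Primary endpoint assessment: TFBUT". SAP section 3 writes it into the rule: "The FAS will include all randomized subjects who have at least 1 post-baseline primary endpoint (TFBUT) assessment".

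**What the FAS decides.** Protocol section 11.2 has "the FAS providing the primary inference for the superiority hypotheses". SAP section 5.3 says the same of the secondary endpoints: "The analysis set for the secondary efficacy assessments will be the FAS". One of these, in SAP section 5.1, is change from baseline in Global Ocular Discomfort VAS at Day 35.

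**The only alternative set.** The sensitivity analysis of the secondary endpoints is: "As a sensitivity analysis, the analysis will be repeated for the PPS using the same model". The PPS is drawn from the FAS: "The PPS will consist of FAS subjects who satisfy all inclusion/exclusion criteria and who have no major protocol deviations".

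**Visit order.** In protocol sections 10.2.2.2 and 10.2.2.3, the "Ocular Discomfort questionnaire" is step 3, the in-clinic drop of masked product is step 5, and TFBUT is in step 6.

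**The concern.** The rule makes use of a recorded VAS conditional on a different measurement. For TFBUT this costs nothing, since a subject with no post-baseline TFBUT adds no outcome to the TFBUT model. For VAS it can remove an observed outcome before the model sees it. The planned MMRM rests on a missing-at-random argument (protocol section 11.5), whose strength is that it uses all observed data. SAP section 3 also says that the FAS is meant to be nearly complete and to stay close to intention to treat. For VAS the rule works against that aim.

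At stake is one of the two remaining secondary hypotheses, since SAP section 11.1 reduces LLT to a listing. Under the Hochberg procedure in SAP section 5.3.1 the two are linked. If VAS has the larger p-value and TFBUT superiority has a one-sided p between 0.0125 and 0.025, the TFBUT claim stands only if VAS falls below 0.025. The VAS analysis set can therefore affect the TFBUT superiority claim too.

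**Working it through.** **1. Where an affected subject would appear**

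| Output | Set | Subject with VAS but no TFBUT |
|---|---|---|
| VAS superiority, main (SAP Table 5-1) | FAS | excluded |
| VAS superiority, sensitivity (SAP Table 5-1) | PPS, within FAS | excluded |
| Post-baseline VAS summaries (SAP 5.3) | PPS and FAS | excluded |
| Listing of observed values (SAP 5.3) | Randomized Set | included |
| Baseline tables (SAP 4.2) | RS, FAS, PPS, Safety | included in RS |

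No row is both a VAS comparison and open to this subject.

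**2. How such a subject could arise**

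The subject needs a post-baseline VAS and no TFBUT reading at any post-baseline visit. The numbered steps put the questionnaire before the drop and before TFBUT, so a visit cut short can yield one without the other. TFBUT could also be missing for an unrelated reason.

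**3. The plan's own figure**

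The documents size only the TFBUT noninferiority test. With SD 2.5, margin 1.0, one-sided 0.025 and 80% power, n per arm = 2 × (1.960 + 0.842)² × 2.5² / 1.0² = 98.1, so 99 per arm or 198 in total. The noncentral t gives 200, as stated, and reproduces all six entries of protocol Table 11-1. None of this changes here. The documents give no SD or effect for VAS, so what follows is illustration only.

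**4. Precision lost**

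Inputs: 220 randomised 1:1 (protocol section 11.10); k excluded, from 0 to 20, where 20 is the whole planned difference between 220 randomised and 200 evaluable. SE ratio = √(220/(220 − k)). Power is for an assumed VAS effect that would have 80% power with all 220.

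- k = 2: SE up 0.5%, power 79.6%
- k = 5: SE up 1.2%, power 79.1%
- k = 20: SE up 4.9%, power about 76%

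**5. Shift in the estimated difference**

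Assume that all k are in one arm of 110 and differ from the rest of that arm by δ SD. Shift = (k/110) × δ. SE of the difference = √(2/110) = 0.135 SD. A subject with only a Day 15 VAS acts on the Day 35 estimate only through the Day 15 to Day 35 covariance; with an assumed regression slope of 0.5, the shift halves.

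| k | δ (SD) | Shift (SD) | Shift (SE), Day 35 VAS present | Shift (SE), Day 15 VAS only |
|---|---|---|---|---|
| 0 | any | 0 | 0 | 0 |
| 2 | 0.5 | 0.009 | 0.07 | 0.03 |
| 2 | 1.0 | 0.018 | 0.13 | 0.07 |
| 5 | 0.5 | 0.023 | 0.17 | 0.08 |
| 5 | 1.2 | 0.055 | 0.40 | 0.20 |
| 20 | 0.5 | 0.091 | 0.67 | 0.34 |

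The last row is a ceiling, not an expectation: it puts the whole planned loss in one arm and gives every one of those subjects a VAS but no TFBUT.

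**The case against.** The strongest reply is that the group is close to empty by design. VAS and TFBUT are both scheduled at Visit 2, Visit 3 and Early Exit. In protocol Table 2-1 they carry the same Early Exit marker, and the last note under the table, which seems to be the one intended, requires at least 14 days on masked treatment. Early-exit data are assigned to a planned visit (SAP section 2.4.1), and one of three readings is enough for a TFBUT value (SAP section 5.1). This stands, and it limits the size of the point.

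A reader might infer more: that subjects who find the drop uncomfortable will refuse it, miss TFBUT and have poor VAS scores discarded, so that the less well tolerated product is flattered. The documents do not support this. Nothing says that TFBUT is omitted when the drop is refused. Only the Screening list is expressly to be done in its stated order; otherwise order is left to a manual of procedures that is not available. A subject who cannot tolerate the product may leave through Early Exit, where no instillation is scheduled. TFBUT may also be missing for reasons unrelated to discomfort or arm.

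Two further replies stand in part. The SAP will report how many subjects are excluded from the FAS, with reasons, so affected subjects would be visible, though not analysed. And a VAS-based set still requires a post-baseline measurement, so it does nothing for subjects who leave before 14 days, when neither measure is scheduled.

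A single common set for both Hochberg-tested endpoints is a tidy choice, but it does not give identical Ns. An FAS subject with no post-baseline VAS already contributes nothing to the VAS model.

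**Conclusion.** The point holds as a matter of set definition. A usable VAS outcome can be set aside because TFBUT is missing, and no planned VAS comparison recovers it.

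Its effect is probably small and may be zero. The shifts of 0.07 to 0.40 SE for 2 to 5 subjects rest on an assumed count, an assumed difference, all affected subjects being in one arm, and a Day 35 VAS being present; they roughly halve if only Day 15 is recorded and the slope is 0.5. The direction cannot be stated from the documents.

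The primary noninferiority test, the data in the TFBUT superiority analysis and the sample size are untouched; the only route to a TFBUT claim is the Hochberg link. This is a minor, low-cost improvement, not a flaw that threatens the trial's main conclusion.

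**What to change.** In SAP sections 3 and 5.3:

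- Run the VAS superiority MMRM on all randomised subjects, analysed as randomised, who have a baseline VAS and at least one post-baseline VAS.
- Keep the TFBUT-based FAS for the TFBUT analyses.
- Report by arm how many subjects had a post-baseline VAS but no post-baseline TFBUT.

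Protocol section 11.2 should carry the same wording if the protocol is amended. SAP section 11.1 records that, at Version 3.0, follow-up was complete, the database was not locked, the treatment code was unbroken, and a protocol amendment had been judged unnecessary for the LLT change. A masked SAP edit was therefore feasible at that point.

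The cost is a sentence or two in the SAP, one analysis flag and one count by arm. The downside is that N may differ by a few subjects between the TFBUT and VAS tables, which a footnote can explain.
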